5.0 METHODOLOGY

5.1 Study Population

Diagnosis/Condition for Entry into the Trial

Patients with metastatic or recurrent histologically confirmed cervical carcinoma who have progressed on or after first line standard of care treatment.

Prospective approval of protocol deviations to recruitment and enrollment criteria, also known as protocol waivers or exemptions, is not permitted.

Each patient should meet all of the inclusion criteria and none of the exclusion criteria for this study in order to be assigned to the study intervention. Under no circumstances, can there be exceptions to this rule. Patients who do not meet the entry requirements are screen failures.

5.1.1 Participant Inclusion Criteria

Participants are eligible to be included in the study only if all of the following criteria apply:

1. Female participants who are at least 18 years of age on the day of signing informed consent with histologically confirmed diagnosis of cervical carcinoma will be enrolled in this study.
2. Cervical cancer is a disease of the female genital tract. No male patients will be enrolled.
3. A female participant is eligible to participate if she is not pregnant (see Appendix 3), not breastfeeding, and at least one of the following conditions applies:
 - a. Not a woman of childbearing potential (WOCBP) as defined in Appendix 3
OR
 - b. A WOCBP who agrees to follow the contraceptive guidance in Appendix 3 during the treatment period and for at least 120 days after the last dose of study treatment.
4. Participant must have recurrent cervical cancer and have a low potential for cure with radiation therapy or surgery alone and:
 - a. May have received up to 2 prior chemotherapy regimens. Platinum sensitizing agents for radiation therapy are considered a chemotherapy regimen.
5. The participant (or legally acceptable representative if applicable) provides written informed consent for the trial, which includes compliance with the requirements and restrictions listed in the informed consent form (ICF) and this protocol.
6. Have measurable disease based on RECIST 1.1. Lesions situated in a previously irradiated area are considered measurable if progression has been demonstrated in such lesions.
7. Have provided archival tumor tissue sample or newly obtained core or excisional biopsy of a tumor lesion not previously irradiated. Formalin-fixed, paraffin embedded (FFPE) tissue blocks are preferred to slides. Newly obtained biopsies are preferred to archived tissue.

8. Have an Eastern Cooperative Oncology Group (ECOG) performance status of 0 to 1. Evaluation of ECOG is to be performed prior to the first dose of treatment.
9. Patient's life expectancy ≥ 16 weeks.
10. Have adequate organ function as defined in the following table (Table 1). Specimens must be collected within 10 days prior to the start of study treatment. Before patients can be enrolled, they must have normal laboratory values as outlined in Table 1. Labs must also fall within normal limits prior to infusion.

Table 1 Adequate Organ Function Laboratory Values

System	Laboratory Value
Hematological	
Absolute neutrophil count (ANC)	$\geq 1500/\mu\text{L}$
Platelets	$\geq 100\,000/\mu\text{L}$
Hemoglobin	$\geq 9.0\text{ g/dL}$ or $\geq 5.6\text{ mmol/L}^{\text{a}}$
Renal	
Creatinine OR Measured or calculated ^b creatinine clearance (GFR can also be used in place of creatinine or CrCl)	$\leq 1.5 \times \text{ULN}$ OR $\geq 30\text{ mL/min}$ for participant with creatinine levels $>1.5 \times$ institutional ULN
Hepatic	
Total bilirubin	$\leq 1.5 \times \text{ULN}$ OR direct bilirubin $\leq \text{ULN}$ for participants with total bilirubin levels $>1.5 \times \text{ULN}$
AST (SGOT) and ALT (SGPT)	$\leq 2.5 \times \text{ULN}$ ($\leq 5 \times \text{ULN}$ for participants with liver metastases)
Coagulation	
International normalized ratio (INR) OR prothrombin time (PT) Activated partial thromboplastin time (aPTT)	$\leq 1.5 \times \text{ULN}$ unless participant is receiving anticoagulant therapy as long as PT or aPTT is within therapeutic range of intended use of anticoagulants
ALT (SGPT)=alanine aminotransferase (serum glutamic pyruvic transaminase); AST (SGOT)=aspartate aminotransferase (serum glutamic oxaloacetic transaminase); GFR=glomerular filtration rate; ULN=upper limit of normal.	
^a Criteria must be met without erythropoietin dependency and without packed red blood cell (pRBC) transfusion within last 2 weeks.	
^b Creatinine clearance (CrCl) should be calculated per institutional standard.	
Note: This table includes eligibility-defining laboratory value requirements for treatment; laboratory value requirements should be adapted according to local regulations and guidelines for the administration of specific chemotherapies.	

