2.2 Trial Schema

2.3 Schedule of Activities

Trial Period:	Screening Phase	Treatment Cycles ^a								End of Treatment	Post-Treatment		
		1	2	3	4	To be repeated beyond 8 cycles					Discon	Safety Follow-up	Follow Up Visits ^b
Treatment Cycle/Title:	Screening					5	6	7	8				
Scheduling Window (Days):	-28 to -1		± 3	± 3	± 3	± 3	± 3	± 3	± 3	At time of Discon ±7	30 days post discon ±7	Every 8 weeks post discon ± 7	Every 12 weeks ±7
Administrative Procedures													
Informed Consent	X												
Inclusion/Exclusion Criteria	X												
Demographics	X												
Medical History	X	X	X	X	X	X	X	X	X				

Trial Period:	Screening Phase	Treatment Cycles ^a								End of Treatment	Post-Treatment			
		1	2	3	4	To be repeated beyond 8 cycles					Safety Follow-up	Follow Up Visits ^b	Survival Follow-Up	
Treatment Cycle/Title:	Screening	1	2	3	4	5	6	7	8	Discon	At time of Discon ±7	30 days post discon ±7	Every 8 weeks post discon ± 7	Every 12 weeks ±7
Scheduling Window (Days):	-28 to -1		± 3	± 3	± 3	± 3	± 3	± 3	± 3					
Prior and Concomitant Medication Review	X	X	X	X	X	X	X	X	X					
Trial Treatment Administration		X	X	X	X	X	X	X	X					
Post-study anticancer therapy status												X	X	
Survival Status												X	X	X
Clinical Procedures/Assessments														
Review Adverse Events			X	X	X	X	X	X	X					
Full Physical Examination	X													
Directed Physical Examination			X	X	X	X	X	X	X					
Vital Signs and Weight	X	X	X	X	X	X	X	X	X					
ECOG Performance Status	X	X	X	X	X	X	X	X	X					
Laboratory Procedures/Assessments: analysis performed by LOCAL laboratory														
Pregnancy Test – Urine or Serum β-HCG	X ^c													
PT/INR and aPTT	X ^a													
CBC with Differential	X ^a	X ^b	X	X	X	X	X	X	X					
Comprehensive Serum Chemistry Panel	X ^a	X ^b	X	X	X	X	X	X	X					
Urinalysis	X ^a													
T3, FT4 and TSH	X ^a				X			X ^f						
Efficacy Measurements														
Tumor Imaging	X				X					X ^d	X			
Tumor Biopsies/Archival Tissue Collection/Correlative Studies Blood														
Archival or Newly Obtained Tissue Collection	X ^e													
Correlative Studies Stool Collection	X ^e				X ^e					X ^e				

^a Must be performed within 10 days of the first treatment visit (Cycle 1 Day 1).

^b Hematology (CBC with differential) and Creatinine results must be available and reviewed by the Investigator prior to infusion. A spot creatinine result may be used to proceed with treatment, as Chemistry results may not be available.

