6.1.3.2 Bone marrow or blood cytogenetic samples

Bone marrow or blood cytogenetic samples may be collected for patients with prolonged hematological toxicities as defined in Section 8.4.7 per routine medical oncology at Miami Cancer Institute.

Bone marrow analysis should include an aspirate for cellular morphology, cytogenetic analysis and flow cytometry, and a core biopsy for bone marrow cellularity. If it is not possible to conduct cytogenetic analysis or flow cytometry on the bone marrow aspirate, then attempts should be made to carry out the tests on a blood sample. Full reports must be provided by the investigator for documentation on the Patient Safety database. These data are not required to be entered into CRF.

Laboratory tests for screening or entry into the Second Course Phase should be performed within 10 days prior to the first dose of treatment. After Cycle 1, pre-dose laboratory procedures can be conducted up to 72 hours prior to dosing. Results must be reviewed by the investigator or qualified designee and found to be acceptable prior to each dose of trial treatment.

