6.2.1.1 Management of hematological toxicity

Management of anemia

Table 12 Management of anemia

Hemoglobin	Action to be taken
Hb < 10 but \geq 8 g/dl (CTCAE Grade 2)	
First occurrence: Give appropriate supportive treatment and investigate causality. Investigator judgement to continue olaparib with supportive treatment (eg transfusion) or interrupt dose for a maximum of 4 weeks. Study treatment can be restarted if Hb has recovered to > 9 g/dl.
 
Subsequent occurrences: If Hb < 10 but \geq 9 g/dl investigator judgement to continue olaparib with supportive treatment (eg transfusion) or dose interrupt (for max of 4 weeks) and upon recovery dose reduction may be considered (to 250 mg twice daily as a first step and to 200 mg twice daily as a second step). If Hb < 9 but \geq 8 g/dl, dose interrupt (for max of 4 weeks) until Hb \geq 9 g/dl and upon recovery dose reduction may be considered (to 250 mg twice daily as a first step and to 200 mg twice daily as a second step).

Hb < 8 g/dl (CTCAE Grade 3)	
Give appropriate supportive treatment (e.g. transfusion) and investigate causality. Interrupt olaparib for a maximum of 4 weeks until improved to Hb \geq 9 g/dl. Upon recovery dose reduce to 250 mg twice daily as a first step and to 200 mg twice daily as a second step in the case of repeat Hb decrease.

Common treatable causes of anemia (e.g., iron, vitamin B12 or folate deficiencies and hypothyroidism) should be investigated and appropriately managed. In some cases, management of anemia may require blood transfusions. For cases where patients develop prolonged hematological toxicity (\geq 2 week interruption/delay in study treatment due to CTC grade 3 or worse anemia and/or development of blood transfusion dependence), refer to guidance later in this section for the management of this.

Management of neutropenia, leukopenia and thrombocytopenia

Table 13 Management of neutropenia, leukopenia and thrombocytopenia

Toxicity	Study treatment dose adjustment
CTCAE Grade 1-2	Investigator judgement to continue treatment or if dose interruption, this should be for a maximum of 4 weeks; appropriate supportive treatment and causality investigation
CTCAE Grade 3-4	Dose interruption until recovered to CTCAE gr 1 or better for a maximum of 4 weeks. If repeat CTCAE grade 3-4 occurrence, dose reduce olaparib to 250 mg twice daily as a first step and 200 mg twice daily as a second step

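### Criterion 10 does not say which infusions or which laboratory limits its pre-infusion sentence covers, and schedule footnote b does not fit the review rule in Section 6.1.3.2

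*Combined protocol and SAP*

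**What the plan says.** Four sets of instructions bear on laboratory results before an infusion.

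- **Section 5.1.1, criterion 10.** Specimens are to be taken within 10 days before study treatment starts. Then: "Before patients can be enrolled, they must have normal laboratory values as outlined in Table 1". The next and last sentence is: "Labs must also fall within normal limits prior to infusion". It gives no cycle, no list of tests and no grade.
- **Section 2.3, footnote b.** "Hematology (CBC with differential) and Creatinine results must be available and reviewed by the Investigator prior to infusion". It continues: "A spot creatinine result may be used to proceed with treatment, as Chemistry results may not be available". In the schedule as extracted, the mark b sits on the Cycle 1 cells for CBC and chemistry; later cycles carry a plain X.
- **Section 6.1.3.2, last paragraph.** After Cycle 1, pre-dose tests may be done up to 72 hours ahead. Then: "Results must be reviewed by the investigator or qualified designee and found to be acceptable prior to each dose of trial treatment". The standard for acceptable is not defined.
- **Toxicity tables.** Table 4 (Section 5.2.2) governs pembrolizumab. It continues the drug in Grade 2-4 hypothyroidism and Grade 2 hyperthyroidism, and with a normal baseline its lowest AST/ALT trigger for withholding is above 3.0 x ULN. Table 13 (Section 6.2.1.1) says of Grade 1-2 neutropenia, leukopenia and thrombocytopenia: "Investigator judgement to continue treatment or if dose interruption, this should be for a maximum of 4 weeks". Table 12 covers anemia and olaparib.

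The protocol does not say which instruction prevails.

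**The concern.** A site holding a mildly abnormal result on an infusion day can find one sentence that bars the infusion and another that allows treatment to go on. A site waiting for the chemistry panel can find one sentence that lets it proceed and another that requires results to be reviewed first. Section 5.1 allows no exceptions to the entry criteria, so a site cannot simply set part of criterion 10 aside.

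The trial is multi-center (Section 2.1), and Section 7.2 plans summaries of dose interruptions and relative dose intensity. If sites resolve the conflict differently, the difference enters those summaries and the deviation record, and pre-dose safety checks are not uniform.

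**Working it through.** The plan gives no figure on this point, so the check sets the passages side by side under each reading of criterion 10.

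**Reading A: every infusion, laboratory reference range.** Any out-of-range value bars infusion. Table 4 continues pembrolizumab in Grade 2-4 hypothyroidism and Grade 2 hyperthyroidism, and Section 2.3 schedules T3, FT4 and TSH on study. A participant with such an event and out-of-range thyroid tests is to continue under Table 4 and may not be infused under criterion 10. This is a direct conflict about the same drug.

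**Reading B: every infusion, Table 1 limits.** The sentence before ties normal values to Table 1, so this is the more natural meaning of the term. In common units, 1500/µL = 1.5 x 10^9/L and 100 000/µL = 100 x 10^9/L. Section 6.2.1.1 gives the Grade 3 bounds as ANC below 1 and platelets below 50 x 10^9/L, so values at or above them are at most Grade 2.

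| Test | Table 1 limit | On-treatment rule | Where they part |
|---|---|---|---|
| ANC (10^9/L) | at least 1.5 | Table 13: may continue at Grade 1-2, i.e. 1.0 or more | 1.0 to <1.5 |
| Platelets (10^9/L) | at least 100 | Table 13: may continue at Grade 1-2, i.e. 50 or more | 50 to <100 |
| AST/ALT (x ULN), normal baseline, no liver metastases | at most 2.5 | Table 4: withholding starts above 3.0 | >2.5 to 3.0 |

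The first two rows are conflicts if treatment in Table 13 includes the infusion. The third is a difference in strictness: Table 4 requires no action in that window but does not say that infusion must go ahead. The row excludes liver metastases because Table 1 sets a wider limit, 5 x ULN, "for participants with liver metastases".

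**Reading C: first infusion only.** Tables 4 and 13 deal with toxicity on treatment, so their conflict with criterion 10 disappears.

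**Footnote b against Section 6.1.3.2.** This comparison does not depend on how criterion 10 is read. Footnote b makes only CBC and creatinine a condition of infusion and accepts that other chemistry, including bilirubin and AST/ALT, may be outstanding. Section 6.1.3.2 requires results to be judged acceptable before each dose, and a result that has not come back cannot be judged. If the mark b is confined to Cycle 1, the mismatch is confined to the first infusion. There, chemistry from screening, taken within 10 days, is on file, but the schedule also lists a Cycle 1 panel and no passage says that the screening panel stands in for it.

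**Error rates.** The design in Section 7.2 rests on 48 patients, a cut-off of 10 responses and response rates of 0.130 and 0.280. None of these depends on the pre-infusion rule.

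**The case against.** The strongest defense is that the passages can be read as a coherent set: criterion 10 for entry and the first infusion, footnote b for Cycle 1 logistics, Section 6.1.3.2 for later doses, and the toxicity tables for events on treatment. Criterion 10 is an eligibility criterion, its specimens are tied to the start of treatment, and the note to Table 1 describes the values as eligibility-defining. This reading is plausible and would remove the conflict with Tables 4 and 13. But the protocol does not state it, and Section 6.1.3.2 speaks of each dose without excluding the first.

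Several stronger inferences are tempting and should not be drawn:

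- **That every infusion, up to 35 per participant, is affected.** This takes one unstated reading of criterion 10 as settled.
- **That footnote b permits dosing with liver tests unknown and so defeats the Table 4 thresholds.** Creatinine is still required, the mark appears on the Cycle 1 cells where recent screening chemistry exists, and Table 4 can still be applied once results return.
- **That Table 12 contradicts criterion 10 at hemoglobin 8 to <9 g/dL.** The Table 12 text concerns continuing olaparib, an oral drug, whereas criterion 10 speaks of infusion. Holding one while continuing the other is not a contradiction.

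A related caution applies to Table 13. Its Grade 1-2 row refers to treatment without naming a drug, but its Grade 3-4 row names olaparib for dose reduction. The thyroid rows of Table 4 are therefore the cleanest conflict about the infusion itself, and they apply only under the reference-range reading, since Table 1 lists no thyroid test.

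**Conclusion.** The point holds as an unresolved inconsistency in the pre-dose rules. Criterion 10 leaves both its scope and its limits open. Applied to every infusion, it conflicts with Table 4 under a reference range, or with Table 13 under Table 1 limits, and in the second case it is also stricter than the Table 4 AST/ALT trigger. Applied to the first infusion only, it does not conflict with the toxicity tables. Under both scopes, footnote b and Section 6.1.3.2 differ on whether treatment may proceed with part of the chemistry outstanding.

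The consequence is operational and concerns consistency of safety practice: delays, deviations and differences between sites. How often it would arise cannot be derived from the documents. Sample size and error rates do not change.

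The conclusion assumes that Section 6.1.3.2 includes the first dose, that Table 13 covers the infusion as part of study treatment, and that the extracted schedule places the mark b correctly. If footnote b is meant for all cycles, its mismatch with Section 6.1.3.2 extends to all of them.

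**What to change.** Reconcile criterion 10, footnote b of Section 2.3, Section 6.1.3.2 and Tables 4, 12 and 13 into one pre-infusion rule. It should state:

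1. which infusions it covers;
2. which results must be available and reviewed before each of them, and whether screening chemistry serves for Cycle 1;
3. which limits apply on study, for which drug, and how they relate to the toxicity tables.

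The limits are for the sponsor to decide; this review takes no position on them. The cost is a change of protocol wording, with no effect on sample size or the analysis.

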5.1.2 Participant Exclusion Criteria

Participants are excluded from the study if any of the following criteria apply:

1. A WOCBP who has a positive urine pregnancy test within 72 hours prior to the first dose of treatment (see Appendix 3). If the urine test is positive or cannot be confirmed as negative, a serum pregnancy test will be required.
2. Note: in the event that 72 hours have elapsed between the screening pregnancy test and the first dose of study treatment, another pregnancy test (urine or serum) must be performed and must be negative in order for subject to start receiving study medication.
3. Has received prior therapy with an anti-PD-1, anti-PD-L1, or anti-PD-L2 agent or with an agent directed to another stimulatory or co-inhibitory T-cell receptor (eg, CTLA-4, OX-40, CD137).
4. Has received prior systemic anti-cancer therapy including investigational agents within 4 weeks prior to the first dose of treatment.

Note: Participants must have recovered from all AEs due to previous therapies to \leq Grade 1 or baseline. Participants with \leq Grade 2 neuropathy may be eligible.

Note: If participant received major surgery, they must have recovered adequately from the toxicity and/or complications from the intervention prior to starting study treatment.

Patients receiving any systemic chemotherapy or radiotherapy (except for palliative reasons) within 3 weeks prior to study treatment

5. Has received prior radiotherapy within 2 weeks of start of study intervention. Participants must have recovered from all radiation-related toxicities, not require corticosteroids, and not have had radiation pneumonitis. A 1-week washout is permitted for palliative radiation (\leq 2 weeks of radiotherapy) to non-CNS disease.
6. Has received a live vaccine within 30 days prior to the first dose of study drug. Examples of live vaccines include, but are not limited to, the following: measles, mumps, rubella, varicella/zoster (chicken pox), yellow fever, rabies, *Bacillus Calmette–Guérin (BCG)*, and typhoid vaccine. Seasonal influenza vaccines for injection are generally killed virus vaccines and are allowed; however, intranasal influenza vaccines (eg, *FluMist®*) are live attenuated vaccines and are not allowed.
7. Is currently participating in or has participated in a study of an investigational agent or has used an investigational device within 4 weeks prior to the first dose of study intervention.

Note: Participants who have entered the follow-up phase of an investigational study may participate as long as it has been 4 weeks after the last dose of the previous investigational agent.

8. Concomitant use of known strong CYP3A inhibitors (eg. itraconazole, telithromycin, clarithromycin, protease inhibitors boosted with ritonavir or cobicistat, indinavir, saquinavir, nelfinavir, boceprevir, telaprevir) or moderate CYP3A inhibitors (eg. ciprofloxacin, erythromycin, diltiazem, fluconazole, verapamil). The required washout period prior to starting olaparib is 2 weeks.
9. Concomitant use of known strong (eg. phenobarbital, enzalutamide, phenytoin, rifampicin, rifabutin, rifapentine, carbamazepine, nevirapine and St John's Wort) or moderate CYP3A inducers (eg. bosentan, efavirenz, modafinil). The required washout period prior to starting olaparib is 5 weeks for enzalutamide or phenobarbital and 3 weeks for other agents.
10. Major surgery within 2 weeks of starting study treatment and patients must have recovered from any effects of any major surgery.
11. Has a diagnosis of immunodeficiency or is receiving chronic systemic steroid therapy (in dosing exceeding 10 mg daily of prednisone equivalent) or any other form of immunosuppressive therapy within 7 days prior to the first dose of study drug.
12. Has a history of a second malignancy, unless potentially curative treatment has been completed with no evidence of malignancy for ≥ 5 years except: adequately treated non-melanoma skin cancer, curatively treated *in situ* cancer of the cervix, ductal carcinoma *in situ* (DCIS), Stage 1, grade 1 endometrial carcinoma.

*Note: The time requirement does not apply to participants who underwent successful definitive resection of basal cell carcinoma of the skin, squamous cell carcinoma of the skin, superficial bladder cancer, *in situ* cervical cancer, or other *in-situ* cancers*

13. Has known active CNS metastases and/or carcinomatous meningitis. Participants with previously treated brain metastases may participate provided they are radiologically stable, i.e. without evidence of progression for at least 4 weeks by repeat imaging (note that the repeat imaging should be performed during study screening), clinically stable and without requirement of steroid treatment for at least 14 days prior to first dose of study intervention.

Patients with symptomatic uncontrolled brain metastases. A scan to confirm the absence of brain metastases is not required. The patient can receive a stable dose of corticosteroids before and during the study as long as these were started at least 4 weeks prior to treatment. Patients with spinal cord compression unless considered to have received definitive treatment for this and evidence of clinically stable disease for 28 days.

14. Has severe hypersensitivity (\geq Grade 3) to pembrolizumab and/or any of its excipients, or patients with a known hypersensitivity to olaparib or any of the excipients of the product.
15. Has active autoimmune disease that has required systemic treatment in the past 2 years (i.e. with use of disease modifying agents, corticosteroids or immunosuppressive drugs). Replacement therapy (eg., thyroxine, insulin, or physiologic corticosteroid replacement therapy for adrenal or pituitary insufficiency, etc.) is not considered a form of systemic treatment and is allowed.

16. Has a history of (non-infectious) pneumonitis that required steroids or has current pneumonitis.
17. Has an active infection requiring systemic therapy.
18. Has a known history of Human Immunodeficiency Virus (HIV) infection.

Note: No HIV testing is required unless mandated by local health authority.

Immunocompromised patients, e.g., patients who are known to be serologically positive for human immunodeficiency virus (HIV), solid organ, and hematopoietic transplant patients.

19. Has a known history of Hepatitis B (defined as Hepatitis B surface antigen [HBsAg] reactive) or known active Hepatitis C virus (defined as HCV RNA [qualitative] is detected) infection.

Note: No testing for Hepatitis B and Hepatitis C is required unless mandated by local health authority.

Patients with known active hepatitis (i.e. Hepatitis B or C).

- Active hepatitis B virus (HBV) is defined by a known positive HBV surface antigen (HBsAg) result. Patients with a past or resolved HBV infection (defined as the presence of hepatitis B core antibody and absence of HBsAg) are eligible.
- Patients positive for hepatitis C virus (HCV) antibody are eligible only if polymerase chain reaction is negative for HCV RNA.

20. Has a known history of active TB (Bacillus Tuberculosis).
21. Has a history or current evidence of any condition, therapy, or laboratory abnormality that might confound the results of the study, interfere with the subject's participation for the full duration of the study, or is not in the best interest of the subject to participate, in the opinion of the treating investigator.

Patients considered a poor medical risk due to a serious, uncontrolled medical disorder, non-malignant systemic disease or active, uncontrolled infection. Examples include, but are not limited to, uncontrolled ventricular arrhythmia, recent (within 3 months) myocardial infarction, uncontrolled major seizure disorder, unstable spinal cord compression, superior vena cava syndrome, extensive interstitial bilateral lung disease on High Resolution Computed Tomography (HRCT) scan or any psychiatric disorder that interferes with the requirements of the trial or prohibits obtaining informed consent.

22. Has known psychiatric or substance abuse disorders that would interfere with cooperation with the requirements of the trial.
23. Is pregnant or breastfeeding or expecting to conceive children within the projected duration of the study, starting with the screening visit through 120 days after the last dose of trial treatment.

24. Has had an allogenic tissue/solid organ/bone marrow transplant or double umbilical cord blood transplantation (dUCBT).
25. Resting ECG and EKG indicating uncontrolled, potentially reversible cardiac conditions, as judged by the investigator (eg., unstable ischemia, uncontrolled symptomatic arrhythmia, congestive heart failure, QTcF prolongation >500 ms, electrolyte disturbances, etc.), or patients with congenital long QT syndrome.
26. Persistent toxicities (>Common Terminology Criteria for Adverse Event (CTCAE) V. 5.0 grade 2) caused by previous cancer therapy, excluding alopecia.
27. Patients with myelodysplastic syndrome/acute myeloid leukemia or with features suggestive of MDS/AML.
28. Patients unable to swallow orally administered medication and patients with gastrointestinal disorders likely to interfere with absorption of the study medication.
29. Whole blood transfusions in the last 120 days prior to entry to the study (packed red blood cells and platelet transfusions are acceptable).

